5.2 Inclusion criteria

Patients eligible for inclusion in this study have to meet **all** of the following criteria:

Patient must meet the following laboratory values at the screening visit unless cytopenias are related to CLL:

1. Diagnosis of chronic lymphocytic leukemia (CLL) meeting criteria established in the World Health Organization (WHO) classification of hematologic disorders or International Workshop on Chronic Lymphocytic Leukemia (IWCLL) ([Hallek et al 2018](#)). Variant immunophenotype and prolymphocytic morphology change after diagnosis of CLL is allowed.
2. Age \geq 18 years
3. [REDACTED]
4. Male patients agree to avoid fathering a child as per the ibrutinib package insert

5. Dose escalation:
 - a. On ibrutinib > 1 year following relapse from another approved therapy without achieving a complete response

[figure not shown]
OR
 - b. On ibrutinib following relapse with another approved therapy and the presence of a known ibrutinib resistance mutation (BTK or PLC γ 2) at ≥ 1 variant allele frequency OR $< 1\%$ with two separate measurements at least 4 weeks apart with increasing variant allele frequency.
6. Dose expansion:
 - a. Arm A: On ibrutinib > 1 year following relapse from another approved therapy without achieving a complete response and patients who have received ibrutinib either alone or in combination (or have received ibrutinib continuously with multiple sequential combination partners) as first-line therapy and have failed to achieve a complete response after 1 year.
 - b. Arm B: On ibrutinib following relapse with another approved therapy and patients who have received ibrutinib either alone or in combination (or have received ibrutinib continuously with multiple sequential combination partners) as first-line therapy and the presence of a known ibrutinib resistance mutation at $\geq 1\%$ variant allele frequency OR $< 1\%$ with two separate measurements at least 4 weeks apart with increasing variant allele frequency. *Note: As of Amendment 6, patients will no longer be enrolled into Arm B.
7. Ibrutinib dose:
 - Escalation: Patients must be receiving 420 mg ibrutinib
 - Expansion: Patients may be on a dose of ibrutinib lower than 420 mg. Any dose must have been stable for 2 months prior to the start of study treatment.
8. Absolute Neutrophil Count ≥ 750 cells/ μ L ($0.75 \times 10^9/L$) independent of growth factor support within 7 days of the first dose of VAY736

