6.1.1 Dosing regimen

The dosing cycle is 28 days. Patients will receive ibrutinib once daily continuously and VAY736 by i.v. once every 2 weeks (Days 1 and 15). During the dose escalation part of the study, the dose of ibrutinib will be 420 mg. During the dose expansion part of the study, ibrutinib will be continued at the same dose schedule as tolerated before study enrollment, see exclusion criteria in [Section 5.2](#) for additional information on dose level.

A Q4W dosing schedule may also be evaluated if supported by emerging clinical data (e.g., safety or PK/PD or activity). The escalation of the Q4W dosing schedule will be guided by a separate BLRM. The DLT data available from VAY736 Q2W will be used to derive a MAP prior distribution for the Q4W dosing schedule as described in [Section 10.4.2](#). This decision will be formally documented in dose-escalation meeting minutes and distributed to all study sites.

Table 6-1 Dose and treatment schedule

Study treatments	Pharmaceutical form and route of administration	Dose	Frequency and/or Regimen
VAY736	Powder for solution for infusion	As assigned	Once every 2 weeks or every 4 weeks, as assigned
Ibrutinib	Solid dose (tablet or capsule) for oral use	Dose escalation: 420 mg Dose expansion: 420 mg or highest tolerated dose	Daily (28 day cycles)

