6.2.4 Definitions of dose limiting toxicities (DLTs)

A dose-limiting toxicity (DLT) is defined as an adverse event or abnormal laboratory value assessed as unrelated to disease, disease progression, inter-current illness, or concomitant medications that occurs within the first 28 days of treatment with the combination of VAY736 and ibrutinib and meets any of the criteria included in [Table 6-3](#). National Cancer Institute Common Terminology Criteria for Adverse events (NCI CTCAE) version 4.03 will be used for all grading. For the purpose of dose-escalation decisions, DLTs will be considered and included in the BLRM.

The investigator must notify the Sponsor immediately of any unexpected CTCAE grade ≥ 3 adverse events or laboratory abnormalities. Prior to enrolling patients into a higher dose level, CTCAE grade ≥ 2 adverse events will be reviewed for all patients at the current dose level.

Table 6-3 Criteria for defining dose-limiting toxicities

For the purpose of dose escalation, DLT is defined as:
Any Grade 4 AEs are DLTs with the exception of:
Neutropenia lasting \leq 7 days (G-CSF may be used to treat patients who have developed dose-limiting neutropenia, as per institutional guidelines)
Lymphopenia or Leukopenia unless clinically significant
Electrolyte abnormalities that are not associated with clinical sequelae or deemed to be not clinically significant and are corrected with appropriate management or supplementation within 72 hours of the onset.
Platelet count CTCAE grade 4 lasting \leq 7 days
Thrombocytopenia not associated with clinically significant bleeding
Infection without neutropenia lasting for \leq 7 days
Tumor lysis syndrome (TLS) persisting for \leq 7 days despite optimal treatment
Any Grade 3 AEs are DLTs with the exception of:
Lymphopenia or leukopenia unless clinically significant
Infusion reaction that resolves to \leq Grade 1 within 6 hours.
Infection without neutropenia lasting for \leq 7 days
Febrile neutropenia CTCAE grade 3
Serum lipase and/or serum amylase (asymptomatic) \leq 7 consecutive days
Nausea and vomiting that resolves within 2 days after starting optimal anti-emetic therapy.
Thrombocytopenia without significant bleeding.
Anemia that resolves within 7 days in the absence of transfusion
Isolated AST or ALT for \leq 7 days
Diarrhea that resolves within 2 days after starting optimal anti-diarrhea treatment.
Rash or photosensitivity lasting \leq 7 days despite skin toxicity treatment

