6.3 Dose modifications

6.3.1 Dose modification and dose delay

Dose delays or adjustments are permitted in order to allow the patient to continue study treatment. If during the first cycle of treatment, a patient experiences an AE meeting the criteria for DLT as outlined in [Table 6-3](#), treatment should be held. Following interruption, treatment may resume at a reduced level if the toxicities resolve to grade 1 or to the patient's baseline

value within the timeframes outlined in [Table 6-4](#). If the AE recurs any time after treatment is restarted, treatment must be discontinued. Adverse events that occur outside the first cycle of treatment should be managed as outlined below and in [Table 6-4](#).

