6.3.1.2 Ibrutinib

For patients who do not tolerate treatment with ibrutinib, dose interruptions and/or reductions should be undertaken as directed in the package insert and per institutional standard. Ibrutinib dose should be held if VAY736 is interrupted for toxicity that is not related to infusion reactions and resumed as per package insert following resolution of toxicity.

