6.3.1.3 VAY736 and ibrutinib

Any dose changes must be recorded on the Dosage Administration Record eCRF.

If a patient requires a dose interruption of > 28 days of either VAY736 or ibrutinib from the intended day of the next scheduled dose, then the patient must be discontinued from the study unless otherwise specified in [Section 6.1.5](#). Patients who discontinue the study for a study related adverse event or an abnormal laboratory value must be followed as described in [Section 6.3.2](#).

Table 6-4 Criteria for dose reduction / interruption and re-initiation of VAY736 treatment for adverse drug reactions.

Dose modifications for VAY736	
Worst toxicity CTCAE Grade ^a (value) during a cycle of therapy	
Investigations (Hematologic)	
Neutropenia (ANC)	
Grades 1 -3	Maintain dose level
Grade 4 (ANC < 500/mm3)	Hold VAY736 until ANC $\geq 0.5 \times 10^9/L$, then resume VAY736 at same dose levels (with G-CSF support) or lower dose levels at investigator discretion.
Thrombocytopenia	
Grade 4 (PLT < 25,000/mm3)	Hold VAY736 until \leq Grade 3 then resume VAY736 at same dose levels or lower dose levels at investigator discretion
Febrile neutropenia (ANC < $1.0 \times 10^9/L$, fever $\geq 38.5^{\circ}C$)	Hold VAY736 until ANC $\geq 0.75 \times 10^9/L$, then resume VAY736 at same dose levels (with G-CSF support) or lower dose levels at investigator discretion.
Investigations (Renal)	
Serum creatinine	
Grade 1 (> ULN - 1.5 x ULN)	May maintain dose level
Grade 2 (> 1.5 - 3.0 x ULN)	Delay study treatment until resolved to Grade 1 or baseline If resolved by ≤ 7 days maintain dose level If resolved ≥ 7 days reduce one dose level
Grade 3 (> 3.0 - 6.0 x ULN)	Delay study treatment until resolved to Grade 1 or baseline If resolved by ≤ 7 days maintain dose level If resolved ≥ 7 days reduce dose of VAY736
Grade 4 (> 6.0 x ULN)	Omit dose and discontinue patient from study drug treatments
Investigations (Hepatic)	
Isolated total Bilirubin elevation	
> ULN – 1.5 x ULN	Maintain dose level
> 1.5 - 3.0 x ULN	Omit dose. Monitor LFTs ^b weekly, or more frequently if clinically indicated, until resolved to $\leq 1.5 \times$ ULN. If resolved in ≤ 7 days, then maintain dose level If resolved in > 7 days, then $\downarrow 1$ dose level

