Grade 2	Maintain dose level, but initiate/intensify appropriate skin toxicity therapy (such as antihistamines, topical corticosteroids and low-dose systemic corticosteroids)
Grade 3, despite skin toxicity therapy	Omit dose until resolved to Grade \leq 1, then: If resolved in \leq 7 days, then \downarrow 1 dose level If resolved in $>$ 7 days (despite appropriate skin toxicity therapy), then discontinue patient from study drug treatment
Grade 4, despite skin toxicity therapy	Omit dose Discontinue patient from study drug treatment
Infusion Reaction	
Grade 1	Decrease infusion rate until recovery
Grade 2	Stop infusion Before restarting – pre-medicate as outlined in Section 6.1.2 . Restart infusion at 50% of previous rate under continuous observation. Ensure that there is a minimum observation period of 1 hour prior to restarting the infusion(s) If the AE recurs at the reinitiated slow rate of infusion, and despite pre-medication, then discontinue patient from study
Grade 3 or 4	Discontinue treatment
Other adverse events	
Grade 1 or 2	Maintain dose level
Grade 3 or 4	Hold VAY736 until resolved to \leq Grade 1 or baseline. If toxicity resolves within 7 days, resume at the same dose. If treatment delay is $>$ 7 days and \leq 28 days, restart at lower dose level of the VAY736. If delay is greater than 28 days, discontinue treatment.

All dose modifications should be based on the worst preceding toxicity.

^a Common Toxicity Criteria for Adverse Events (CTCAE Version 4.03)

^b Core LFTs consist of ALT, AST, GGT, total bilirubin (fractionated [direct and indirect], if total bilirubin > 2.0 x ULN), and alkaline phosphatase (fractionated [quantification of isoforms], if alkaline phosphatase > 2.0 x ULN.)

^c "Combined" defined as total bilirubin increase to the defined threshold concurrently with ALT/AST increase to the defined threshold

If combined elevations of AST or ALT and total bilirubin do not meet the defined thresholds, please follow the instructions for isolated elevation of total bilirubin and isolated elevation of AST/ALT, and take a conservative action based on the degree of the elevations (e.g. discontinue treatment at the situation when omit dose is needed for one parameter and discontinue treatment is required for another parameter). After all elevations resolve to the defined thresholds that allow treatment re-initiation, re-start the treatment either at the same dose or at one dose lower if meeting a criterion for dose reduction

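### Table 6-4 lets VAY736 restart after febrile neutropenia on the neutrophil count alone, so a patient with ANC 0.75 to 0.99 who is still febrile may be re-dosed

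*Protocol*

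**What the plan says.** Table 6-4 (protocol Section 6.3.1.3) names the event as "Febrile neutropenia (ANC < $1.0 \times 10^9/L$, fever $\geq 38.5^{\circ}C". The action in the same row is: "Hold VAY736 until ANC $\geq 0.75 \times 10^9/L$, then resume VAY736 at same dose levels (with G-CSF support) or lower dose levels". The choice between the same and a lower dose is left to the investigator. Temperature does not appear in the restart condition.

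Other parts of the dose-modification rules tie restart to recovery from the event:

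- Section 6.3.1, for an event that meets the DLT criteria in cycle 1: "treatment may resume at a reduced level if the toxicities resolve to grade 1" or to the patient's baseline.
- Table 6-4, other adverse events of Grade 3 or 4: "Hold VAY736 until resolved to \leq Grade 1 or baseline".
- Section 6.3.1.2, for ibrutinib held alongside VAY736: "resumed as per package insert following resolution of toxicity".

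Table 6-3 lists "Febrile neutropenia CTCAE grade 3" among the Grade 3 exceptions, so such an event is not in itself a DLT.

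**The concern.** A hold that starts on two conditions and ends on one can end while the event is still present. Here the two sets overlap: with ANC from 0.75 up to 1.0 and a temperature of 38.5 °C or more, the row calls for a hold and allows a restart. If the count is already in that band at onset, the hold has no minimum length.

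The count threshold is not the fault. Afebrile Grade 1 to 3 neutropenia is dosed through by design, and 0.75 is also the ANC floor for entry (inclusion criterion 8). The missing part is fever.

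What is at stake is whether a B-cell-depleting antibody may be infused into a patient who is febrile and neutropenic. The row does not force the infusion. It leaves the decision to local judgement at the point where a protocol rule would be expected.

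**Working it through.** **1. Trigger against release.** Inputs are the thresholds in Table 6-4.

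| Row | Hold starts | Hold ends | Overlap |
|---|---|---|---|
| Grade 4 neutropenia | ANC < 0.5 | ANC ≥ 0.5 | none |
| Grade 4 thrombocytopenia | platelets < 25,000/mm³ | Grade 3 or better | none |
| Febrile neutropenia | ANC < 1.0 and T ≥ 38.5 °C | ANC ≥ 0.75, any T | 0.75 ≤ ANC < 1.0 and T ≥ 38.5 °C |

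**2. How unusual the row is.** Rows of Table 6-4 that hold a dose and later restart it:

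- Grade 4 neutropenia, Grade 4 thrombocytopenia, febrile neutropenia (3)
- creatinine Grades 2 and 3 (2)
- bilirubin > 1.5–3.0 and > 3.0–10.0 x ULN (2)
- AST/ALT > 5.0–10.0 x ULN with baseline ≤ 3.0, and > 10.0–20.0 x ULN (2)
- amylase/lipase Grade 3 (1)
- hypertension Grade 3 (1)
- diarrhea Grades 2 and 3 (2)
- rash Grade 3 (1)
- other adverse events Grade 3 or 4 (1)

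The total is 3 + 2 + 2 + 2 + 1 + 1 + 2 + 1 + 1 = 15. The Grade 2 infusion reaction row is left out because it pauses an infusion rather than holding a dose. The footnote on indirect bilirubin is a stated exception. The test is whether restart requires the toxicity to leave the row's own range or return to baseline. Fourteen of 15 rows pass. Febrile neutropenia does not, because it addresses one of its two defining conditions.

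**3. Whether another rule closes the gap.**

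- Section 6.3.1 requires resolution, but only for cycle 1 events that meet the DLT criteria. It covers Grade 4 febrile neutropenia in cycle 1. It covers Grade 3 in cycle 1 only if the event leads to a dose reduction, which Table 6-3 counts as a DLT. It covers nothing after cycle 1.
- The row for other adverse events would hold a separately reported Grade 3 or 4 infection, but not fever that is part of an event with its own row.
- Table 6-5 asks for laboratory tests at least weekly and sets no re-dosing condition.
- The Table 6-4 footnotes and the SAP contain nothing on fever.

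The uncovered cases are Grade 3 febrile neutropenia in cycle 1 resumed at the same dose, and any febrile neutropenia in later cycles.

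**4. How often an infusion could fall in the window.** Section 6.1.1 gives "VAY736 by i.v. once every 2 weeks (Days 1 and 15" of a 28-day cycle, with a four-weekly schedule possible. Assume an episode of D days, with onset independent of dosing and infusions on their scheduled days. The chance that the episode covers a scheduled infusion day is D/14 (Q2W) or D/28 (Q4W).

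| D (assumed) | Q2W | Q4W |
|---|---|---|
| 1 day | 1/14 = 7% | 1/28 = 4% |
| 3 days | 3/14 = 21% | 3/28 = 11% |
| 7 days | 7/14 = 50% | 7/28 = 25% |

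These are upper bounds, conditional on an episode, because the ANC must also lie in 0.75 to 0.99 when the dose is given. The documents do not give the frequency of febrile neutropenia, so no absolute risk follows.

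**The case against.** The strongest reply is that a patient with ANC 0.8 and 38.5 °C on the infusion day still meets the row's trigger, so a cautious reader would hold. That reading is available, but the restart condition is met at the same moment. A rule that gives both instructions has not settled the question.

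A second reply is that the comparison depends on the test used. If resolution means Grade 1, baseline or a stated near-normal limit, 12 of 15 rows pass, and the three that fail are the three haematologic rows. That count is right. Even so, the other two haematologic rows release only when the count has left their own trigger range, so the overlap remains specific to this row. Overlap is also possible through the return-to-baseline option: entry allows creatinine below 2 x ULN, which reaches into the Grade 2 range. That, however, returns a patient to a pre-treatment state and does not dose through a new event.

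Third, Section 7.1.3 requires treatment to stop for adverse events that pose a significant safety risk, and an investigator can always withhold a dose. Both are true, but they are general safeguards and supply no fever criterion for restart.

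The points on scale stand. Section 1.3.4 reports no sign that VAY736 lowers neutrophil counts, although neutropenia is among the common ibrutinib reactions. The purpose of the hold is inferred, not stated. The uncovered case needs persisting fever, a count in a narrow band, no separately reported severe infection and an infusion that is due.

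**Conclusion.** The concern holds. As written, the row permits VAY736 to be restarted in a patient who still has febrile neutropenia by the row's own definition, and no other rule prevents it for Grade 3 events in cycle 1 resumed at the same dose or for any such event after cycle 1. This follows from the printed thresholds and needs no outside source. It is the only one of the 15 hold-and-restart rows whose trigger and release overlap in this way, on the test of leaving the row's range or returning to baseline.

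The number of patients affected is probably small and cannot be estimated from the documents. The percentages above rest on assumed episode lengths and random onset, and are ceilings. The point concerns patient safety in dosing. It does not bear on an efficacy estimate or an error rate. It merits correction because the rule permits an unsafe action and the correction is simple.

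**What to change.** Change the restart condition so that VAY736 is held until fever has resolved and ANC is at least 0.75 x 10^9/L, and leave the rest of the row as it is. The limit for resolved fever should be below 38.5 °C, or a lower value set by the sponsor's medical team. A lower value is preferable, since otherwise a patient at 38.4 °C with ANC 0.8 could be dosed. The team should also decide whether to require a minimum afebrile period, and should have the temperature read before any acetaminophen premedication.

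Keep the ANC threshold at 0.75. Raising it to 1.0 could put restart out of reach for patients enrolled with counts of 0.75 to 0.99 and push them into the rule that discontinues after an interruption of more than 28 days. The change also brings the VAY736 restart into line with the ibrutinib rule in Section 6.3.1.2.

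The cost is a short written amendment with the approvals in Section 12.1, and slightly longer holds for some patients. No new type of assessment is needed: body temperature is a protocol vital sign (Section 7.2.2.2) and ANC is part of hematology. Because the short examination from Cycle 2 Day 1 lists only blood pressure and pulse as vital signs (Section 7.2.2.1), the amendment should ask for a temperature reading before restart. SAP Section 1 records that early termination was endorsed on 22-Sep-2023, so the benefit is confined to patients still to be dosed and to any later protocol that reuses this table.

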	Repeat LFTs ^b as soon as possible, preferably within 48-72 hours from awareness of the abnormal results; monitor LFTs ^b weekly, or more frequently if clinically indicated, until resolved to baseline or stabilization over 4 weeks.

Combined ^c elevations of AST or ALT and total bilirubin	
AST or ALT >3.0xULN combined with total bilirubin >2.0 x ULN without evidence of cholestasis ^d	
Permanently discontinue patient from study drug treatment.
 
Repeat as soon as possible, preferably within 48 hours from awareness of the abnormal results, then with weekly monitoring of LFTs^b, or more frequently if clinically indicated, until AST, ALT, or bilirubin have resolved to baseline or stabilization over 4 weeks.

Investigation (metabolic)	
Asymptomatic amylase and/or lipase elevation	
Grades 1-2	Maintain dose level
Grade 3 (> 2.0 - 5.0 x ULN)	
Omit dose until resolved to Grade \leq 1 or baseline then:
 
If resolved in \leq 7 days, then maintain dose level
 
If resolved in > 7 days, then \downarrow 1 dose level

Grade 4 (> 5.0 x ULN)	Omit dose and discontinue patient from study drug treatment.
Vascular disorders	
Hypertension	
CTCAE Grade 3	
Omit dose until resolved to Grade \leq 1 or baseline then:
 
If resolved in \leq 7 days, then maintain dose level
 
If resolved in > 7 days, then \downarrow 1 dose level

CTCAE Grade 4	Omit dose and discontinue patient from study drug treatment
Gastro intestinal	
Pancreatitis	
Grade 2	Maintain dose level
Grade \geq 3	Omit dose and discontinue patient from study drug treatment
Diarrhea**	
Grade 1	Maintain dose level but, initiate anti-diarrhea treatment
Grade 2	
Omit dose until resolved to \leq grade 1, then maintain dose level.
 
If diarrhea returns as \geq grade 2, then omit dose until resolved to \leq grade 1, then \downarrow 1 dose level

Grade 3	
Omit dose until resolved to \leq grade 1, then \downarrow 1 dose level
 
Omit dose until resolved to Grade \leq 1, then:

	If resolved in \leq 7 days, then \downarrow 1 dose level If resolved in $>$ 7 days (despite appropriate therapy), then discontinue patient from study drug treatment
Grade 4	Omit dose Discontinue patient from study drug treatment
Skin and subcutaneous tissue disorders	
Rash/photosensitivity	
Grade 1	Maintain dose level. Consider to initiate appropriate skin toxicity therapy (such as antihistamines, topical corticosteroids and low-dose systemic corticosteroids)

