6.3.2 Follow-up for toxicities

Patients whose treatment is interrupted or permanently discontinued due to an adverse event or clinically significant laboratory value, must be followed up at least once a week (or more frequently if required by institutional practices, or if clinically indicated) for 4 weeks, and subsequently at approximately 4-week intervals, until resolution or stabilization of the event, whichever comes first. Appropriate clinical experts such as ophthalmologist, endocrinologist, dermatologist, psychiatrists etc. should be consulted as deemed necessary.

Table 6-5 outlines the follow-up evaluation recommended for toxicities of specific types and CTCAE grades.

Table 6-5 Follow-up evaluations for selected toxicities

TOXICITY	FOLLOW-UP EVALUATION
Blood and lymphatic system disorders	If CTCAE Grade 4 neutropenia, thrombocytopenia or anemia, or febrile neutropenia occurs, test pertinent labs at least weekly until resolution to baseline or stabilization.
Hepatic	If a hepatic adverse event occurs, ALT, AST and total bilirubin must be measured at least once a week until resolution to CTCAE Grade \leq 1 or baseline. In patients with total bilirubin Grade \geq 2 (any duration) bilirubin should be fractionated into total/direct or indirect/direct components and any additional evaluation as clinically indicated by these results should be performed
Investigations (metabolic)	Test twice weekly until \leq CTCAE grade 2, continue to test weekly until resolution to \leq CTCAE grade 1 or stabilization. Amylase or lipase \geq CTCAE grade 3 A CT scan or equivalent imaging procedure to assess the pancreas, liver, and gallbladder is recommended within 7 days of the first occurrence of any \geq CTCAE grade 3 result, to exclude disease progression or potential other liver disease. In patients with serum triglycerides \geq 500 mg/dL, urine amylase also needs to be tested.
Cardiac disorders QT and ECG ECG changes indicative of ischemic event	Twice weekly ECGs until normalization or stabilization of ECG findings

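### Protocol Table 6-4 tells sites both to keep and to reduce VAY736 when a Grade 2 or Grade 3 serum creatinine rise resolves on exactly day 7

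*Protocol*

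**What the plan says.** Table 6-4 in Protocol Section 6.3.1.3 gives the rules for holding, reducing and restarting VAY736. For serum creatinine Grade 2, treatment is delayed until recovery to Grade 1 or baseline, and then: "If resolved by ≤ 7 days maintain dose level If resolved ≥ 7 days reduce one dose level". The Grade 3 row has the same first branch, and its second branch reads "If resolved ≥ 7 days reduce dose of VAY736".

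Section 6.3.1.1 sends a first reduction to the next lowest safe dose in Table 6-2. It normally allows two reductions per patient. It requires discontinuation if the toxicity returns at the same or worse severity after restarting at a lower dose.

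Section 6.3.2 says that patients whose treatment is interrupted for an adverse event or a clinically significant laboratory value "must be followed up at least once a week" for the first four weeks.

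Dose interruptions, reductions and dose intensity are among the primary tolerability endpoints (Protocol Table 3-1; SAP Section 2.6). SAP Section 2.5.1.5 reports dose reductions for VAY736 only.

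**The concern.** A rule that branches on time should send each duration to one action. Here the two branches share their boundary, and the actions at that boundary are opposite. Two sites could each follow the table and dose the same patient differently for the rest of treatment.

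Day 7 is not a contrived value. A recheck at the minimum frequency in Section 6.3.2 falls one week after the hold, which is where the rows overlap. The choice also has later consequences under Section 6.3.1.1. Only the patient who was reduced has used one of two permitted reductions. Only that patient must stop under that section if the same toxicity returns at the same or worse severity.

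**Working it through.** The plan gives no figure to reproduce. The check evaluates each rule at resolution time t, in days, with particular attention to t = 7.

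**Rows side by side (Table 6-4)**

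| Row | Earlier branch | Later branch | Action at t = 7 |
|---|---|---|---|
| Creatinine Grade 2 | ≤ 7: maintain | ≥ 7: one level down | maintain **and** reduce |
| Creatinine Grade 3 | ≤ 7: maintain | ≥ 7: reduce | maintain **and** reduce |
| Bilirubin > 1.5 to 3.0 × ULN | ≤ 7: maintain | > 7: one level down | maintain |
| Bilirubin > 3.0 to 10.0 × ULN | ≤ 7: one level down | > 7: discontinue | one level down |
| AST/ALT > 5 to 10 × ULN (baseline ≤ 3 × ULN) | ≤ 7: maintain | > 7: one level down | maintain |
| Amylase/lipase Grade 3 | ≤ 7: maintain | > 7: one level down | maintain |
| Hypertension Grade 3 | ≤ 7: maintain | > 7: one level down | maintain |
| Rash Grade 3 despite therapy | ≤ 7: one level down | > 7: discontinue | one level down |

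The six comparison rows each give one action at day 7, always the milder one. Two other rows with a 7-day limit are left out. Diarrhea Grade 3 is uncertain as extracted (see the objection). The row for other Grade 3 or 4 events begins "If toxicity resolves within 7 days, resume at the same dose", but its next branch turns on length of treatment delay rather than time to resolution, so it is not a clean comparator.

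**Search for a tie-break.** Sections 6.3.1 to 6.3.1.3 give no precedence between branches. The table's note on worst preceding toxicity ranks toxicities, and here the toxicity and grade are the same under both branches. The advice in footnote c to act conservatively concerns combined AST/ALT and bilirubin elevations only.

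**Size of one level (Table 6-2: 0.1, 0.3, 1 and 3 mg/kg)**
- 3 to 1 mg/kg: 1 − 1/3 = 66.7% lower
- 1 to 0.3 mg/kg: 1 − 0.3 = 70% lower
- 0.3 to 0.1 mg/kg: 1 − 0.1/0.3 = 66.7% lower

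**Illustrative relative dose intensity (RDI).** Under SAP Sections 2.5.1.3 and 2.5.1.4 the duration of exposure cancels, so RDI is actual over planned cumulative dose. Suppose k of n doses are given at the starting level and the rest at a fraction f of it. Then RDI = [k + (n − k) × f] / n. The assumptions are Q2W dosing, an event after cycle 1, no missed dose, no intermediate level and no re-escalation. n is 12 for six cycles, or 16 for patients who continue VAY736 through Cycle 8.

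| Event | n | f = 1/3 | f = 0.3 |
|---|---|---|---|
| After C2D1 (k = 3) | 12 | (3 + 3)/12 = 0.50 | (3 + 2.7)/12 = 0.475 |
| After C2D1 (k = 3) | 16 | (3 + 4.33)/16 = 0.458 | (3 + 3.9)/16 = 0.431 |
| One dose left (k = 11) | 12 | 11.33/12 = 0.944 | 11.3/12 = 0.942 |
| One dose left (k = 15) | 16 | 15.33/16 = 0.958 | 15.3/16 = 0.956 |

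Under the maintain branch the RDI is 1.00. These figures show what one reduction does to one patient. They do not show how often the overlap is met. In an arm of about 20, one such patient changes the proportion with a reduction by 1/20, or 5 percentage points.

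**The case against.** The strongest reply is that this is a one-symbol slip affecting a single day, in a protocol that already tolerates variation. The Grade 4 neutropenia, Grade 4 thrombocytopenia and febrile neutropenia rows leave the restart dose to the investigator, and Section 6.3.1.1 describes interruptions and reductions as recommended. The documents give no rate for creatinine events. The Amendment 03 rationale does not list creatinine among the most common related events in the first 11 patients, although that list is not exhaustive. All of this stands and keeps the point minor. It does not remove the overlap: those other rows state their discretion openly, while the creatinine rows give two fixed and opposite instructions.

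A PDF reading error is unlikely. The ≥ sign appears in both creatinine rows, while the bilirubin row that follows reads > 7.

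Two stronger readings are tempting, and the documents support neither.

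- **Diarrhea Grade 3.** As extracted, an untimed instruction to reduce sits beside a timed rule that discontinues after more than 7 days. A reader might infer a third conflicting row. However, the cell appears to break across a page, the untimed line repeats the end of the Grade 2 row, and a lost sub-row label could make both lines valid.
- **Dose-limiting toxicity.** Table 6-3 counts any adverse event leading to a reduction in the observation period as a DLT. A reader might infer that the day-7 reading decides DLT status. The header phrase "value) during a cycle of therapy" leaves room for that, but Section 6.3.1 expressly sends events outside cycle 1 to this table. Section 6.2.4 adds that a DLT must be judged unrelated to disease, progression, intercurrent illness or concomitant medication. At Amendment 06, escalation was complete with 15 patients and none ongoing, and the SAP limits the dose-determining set to escalation. No DLT was reported in the first 11 patients.

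**Conclusion.** The creatinine Grade 2 and Grade 3 rows are wrong as written: resolution on exactly day 7 calls for both the same dose and a lower one, with no rule to choose. Confidence in this is high, subject only to a glance at the source table for the two signs.

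The issue is minor. It touches individual VAY736 dosing and descriptive summaries of reductions and dose intensity. Recorded exposure stays correct whichever branch a site followed. No effect on DLTs, the Bayesian logistic regression model or the Cycle 9 response analysis is claimed. The documents do not show that any patient met the overlap, or that anyone is still to receive VAY736: 11 expansion patients were on study treatment at Amendment 06, and the SAP introduction records that early termination has since been endorsed. The RDI figures hold only under their stated assumptions.

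**What to change.** Change ≥ 7 days to > 7 days in both creatinine rows of Table 6-4. Day 7 then falls in the maintain branch, as it does in the other rows where the earlier branch is to maintain.

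- **If VAY736 is still to be given:** make the change by written amendment under Protocol Section 12.1. The cost is two symbols plus sponsor and IRB/IEC approval, and health authority approval where required.
- **If dosing has ended:** no amendment is needed. Check the patient-level dose listing with dose-change reasons that SAP Section 2.5.1.1.1 already plans. Read it alongside the adverse event listing, because a patient restarted at the same dose may show no dose change. Report any patient whose handling turned on day 7, or state that there were none. This needs no new data.

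For diarrhea Grade 3, only compare the row with the source table for a lost sub-row label. No deletion is proposed, since it could remove a valid rule.
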